9.3 POPULATIONS FOR ANALYSIS

9.3.1 TOTAL COHORT

The total cohort, or screened population, includes all participants who provide informed consent and are screened, regardless of whether the participant is randomized or vaccinated. This population will be used to fully account for participant disposition.

9.3.2 SAFETY COHORT

The safety cohort is a subset of the total cohort and will include all participants receiving at least one immunization. Participants will be analyzed according to immunization received. Participants who have received at least one immunization will not be excluded from the safety population for ineligibility, missing follow-up immunization, or protocol deviations.

9.3.3 IMMUNOGENICITY COHORT

The Immunogenicity Population will include all participants completing the immunization series (no missed immunizations) and for whom immunogenicity endpoint data are available. Participants who missed any follow-up immunizations will be excluded in immunogenicity analyses thereafter. Participants will be analyzed according to immunization received.

9.3.4 CHMI (VACCINE EFFICACY) COHORTS

The Intention to Treat (ITT) Population is a subset of the screened population that is deemed eligible to participate in the study, is randomized to a treatment group, and receives 1, 2 or 3 vaccinations. Because individuals will not be permitted to proceed to CHMI if they have not received three vaccinations, the results of CHMI will be imputed in those individuals receiving only one or two immunizations (see sensitivity analysis below).

The Modified ITT Population (mITT) is a subset of the ITT Population that receives all three immunizations and undergoes CHMI. It includes participants to whom V2 and/or V3 are administered out of the pre-specified time window, and also participants receiving partial immunizations, as long as at least 20% of the injectate is administered for each immunization. The mITT Population will be used for the primary analysis of VE.

The According to Protocol (ATP) Population is a subset of the mITT Population where three complete and correct immunizations (all 3 immunizations within the protocol specified time windows and each injection delivering at least 80% of the IP) as well as CHMI were administered within the allowed time windows. The ATP Population will be used for an exploratory analysis of VE.

If a volunteer drops out part way through CHMI, a judgment will be made after CHMI is completed regarding whether the efficacy data can be included, depending on the timing and result of the last PCR sample. If the result of the last (or an earlier) PCR is positive, the volunteer will be included in the efficacy analysis as not protected, using the measured prepatent period. If the result is negative, the volunteer will be included in the efficacy analysis as protected only if this negative result is recorded on the same day (or later) as the day of the most delayed positive result in any of the other volunteer undergoing CHMI.

Volunteers significantly straying from protocol procedures (e.g., use of antimalarial drugs during CHMI as discussed in the section on estimands) will be excluded from primary efficacy analysis but included in the exploratory analysis.

9.4 STATISTICAL ANALYSIS

9.4.1 GENERAL APPROACH

Data collection will be performed on site at the clinical center by direct data entry into eCRFs. Paper versions of the CRFs will be available, if needed, in the event the direct data entry system is unavailable. Paper CRFs, if used, will be retained as source documents and transcribed into the database. Data analysis will be supported by the data management company and will be performed in a coordinated way by study investigators and collaborators from Sanaria.

A Statistical Analysis Plan (SAP) will be prepared and will describe the statistical analyses for the study. The SAP may include minor differences from what is stated in the protocol.

9.4.2 ANALYSIS OF DEMOGRAPHICS

An analysis will be conducted on data and samples collected through 8 weeks post CHMI. Baseline demographics will be assessed using descriptive statistics and presented as tables, figures and listings. Continuous variables will be summarized with mean, standard deviation, median, and range, while categorical variables will be presented as a number and percentage.

9.4.3 ANALYSIS OF EFFICACY

The geometric mean, median, minimum, and maximum time to parasitemia (prepatent period) by qPCR after each CHMI will be presented for the 3-week and 12-week cohorts and for the combined controls. Prepatent periods will be measured from the hour/minute of administration of PfSPZ Challenge (7G8) to the hour/minute when the first positive sample was taken, with the result for the prepatent period calculated as the difference.

Primary efficacy analysis: the primary efficacy endpoint of the study for each research participant will be the presence or absence of Pf7G8 parasitemia following CHMI in the mITT population, defined by positive qPCR testing during the 28 days following CHMI, comparing vaccinees in each group to the combined controls from all the groups. VE will be defined as $(1 - \text{relative risk}) \times 100$.

Secondary efficacy analysis: in the secondary analysis, each cohort will be examined individually for protection. A 2-tailed Fishers exact test will be used to compare vaccinees with the controls. A p value <0.05 will be considered significant. Fishers exact test is appropriate because it is expected that all or nearly all controls will become positive, a non-random outcome.

Exploratory efficacy analysis: The trial is not powered for comparisons between cohorts, although this will be examined as an exploratory outcome. A 2-tailed Barnard's test will be used to compare the proportion of participants in each group who become parasitemic after CHMI. A p value <0.05 will be considered

significant. Barnard's test is appropriate because we have no expectations regarding differences in the proportion of protected study participants undergoing CHMI at 3 or 12 weeks.

A sensitivity analysis will be done by computing VE in the entire group using the ATP population and using the ITT population. In the latter case, CHMI outcome will be imputed first as not protected for all individuals not undergoing CHMI, and then as protected. This will provide an indication of the robustness of the primary VE outcome.

Finally, the VE for each group will be determined by time-to-event analysis (1 minus the hazard ratio). The time at risk will end whenever one of the following conditions happens: diagnosis of malaria infection, withdrawal from the study after receiving CHMI, loss to follow-up, or end of 28 day follow-up period. A Kaplan-Meier analysis with a log-rank test will be used to compare distributions of malaria-free time following CHMI.

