9.2 SAMPLE SIZE DETERMINATION

The primary outcome for these studies will be VE measured as $[1 - \text{risk ratio}] \times 100$. The outcomes of both CHMI's will be combined. Sample sizes of 45 and 15 for the vaccine and placebo groups were selected to be able to show with 83% power, if there are six drop-outs from the vaccine group and two from the control group prior to CHMI, that an infection rate of 92.3% in the controls (12/13 developing parasitemia) and 51% in the vaccinees (20/39 developing parasitemia) is statistically significantly different ($\alpha=0.05$, 2-tailed) (VE=44.4%). As we expect VE to be higher than this, the sample size should be adequate.

Regarding safety, the study provides the following power to identify adverse outcomes:

1. If no PfSPZ Vaccine-related SAEs are observed, the sample size of 45 provides 95% confidence that the true rate of SAEs caused by immunization is less than 6.7%, 90% confidence that the true rate of SAE's is less than 5.0%, 85% confidence that the true rate of SAEs is less than 4.2%, and 80% confidence that the true rate of SAEs is less than 3.5%.
2. With regard to the ability to make comparisons between vaccinees and placebo recipients in the rates of grade 2 and grade 3 adverse events, where significant differences might indicate poor tolerability, a sample size of 45 vaccinees and 15 placebo recipients will show a statistically significant difference ($p<0.05$, two-tailed) between 10/45 vaccinees experiencing poor tolerability on the one hand, and 0/15 controls on the other hand.

Immunogenicity:

Antibody responses (group means, standard deviations, medians and ranges) will be used to compare participants with controls, and to compare infected and non-infected participants, the latter to look for trends suggesting a threshold response above which VE is seen, using appropriate nonparametric tests such as Wilcoxon and Spearman correlation. The data management vendor is providing biostatistical consultation and will generate the Statistical Analysis Plan, which will be finalized in advance of the database lock. The same vendor will conduct the statistical analyses.

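### Fisher's exact test is assigned to the per-timepoint efficacy comparisons for a reason that does not support it, and no test is named for the pooled primary comparison to which the 83% power belongs

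*Combined protocol and SAP*

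**What the plan says.** Section 9.2 gives the power for the combined comparison: "Sample sizes of 45 and 15 for the vaccine and placebo groups were selected to be able to show with 83% power", allowing for six vaccinee and two control drop-outs before CHMI. The planning rates are "an infection rate of 92.3% in the controls (12/13 developing parasitemia) and 51% in the vaccinees (20/39 developing parasitemia"), at a two-sided 5% level. No test is named there.

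Section 9.4.3 has three relevant paragraphs.

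- **Primary.** VE is one minus the relative risk, "comparing vaccinees in each group to the combined controls from all the groups". No test is named.
- **Secondary.** Each cohort is examined on its own with a two-sided Fisher test at 0.05, because "Fishers exact test is appropriate because it is expected that all or nearly all controls will become positive, a non-random outcome". The text speaks only of the controls, without saying whether these are the cohort's own or all of them.
- **Exploratory.** The 3-week and 12-week cohorts are compared with Barnard's test, because "Barnard's test is appropriate because we have no expectations regarding differences in the proportion of protected study participants".

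Section 4.4 describes VE at each timepoint as a powered objective and points to the statistics section. That section gives no per-timepoint power.

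**The concern.** Fisher's test conditions on the total number of infections. The design does not fix that total. Arm sizes are fixed; infections among vaccinees are random, and section 3.1 accepts that some controls may not become parasitemic. A high expected control infection rate leaves the total random. The reason given for Barnard is no better: having no expectation about the direction or size of a difference has no bearing on the choice between a conditional and an unconditional test. Both comparisons are of two independent binomials, so they have the same structure.

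Two things are at stake. The 83% has no test attached, and Fisher, the only proportion test the plan names for vaccinees against controls on efficacy, does not produce it. And the analysis to which Fisher is expressly assigned, which the protocol calls powered, gives up power that an unconditional exact test would keep while still holding the error rate below 5%.

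**Working it through.** **Inputs.** From 9.2: 45 and 15 enrolled, 39 and 13 after drop-out; infection 20/39 = 51.3% and 12/13 = 92.3%; two-sided 0.05. From 4.2: 22 or 23 vaccinees and 7 or 8 controls per cohort. Assumption: drop-out splits about evenly, leaving 19 or 20 vaccinees and 6 or 7 controls per timepoint. From 2.1.3: historical control infection 27/28 = 96.4%.

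**Step 1: reproduce the stated figures.**

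- VE = 1 − 0.5128/0.9231 = 44.4%, as stated.
- Pooled rate = (20 + 12)/52 = 0.6154.
- Null SE = √[0.6154 × 0.3846 × (1/13 + 1/39)] = 0.1558.
- Alternative SE = √[0.9231 × 0.0769/13 + 0.5128 × 0.4872/39] = 0.1089.
- Power = Φ[(0.4103 − 1.96 × 0.1558)/0.1089] = Φ(0.96) = 83.2%. The stated 83% reproduces.

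**Step 2: exact power, primary comparison.** Power is the sum, over all tables (a, b) with p < 0.05, of Bin(a; 13, 12/13) × Bin(b; 39, 20/39). Maximum size is the largest such sum when both arms share one infection rate.

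| Test, 39 v 13 | Power | Maximum size |
|---|---|---|
| Fisher | 79.5% | 3.4% |
| Barnard, pooled score | 82.7% | 4.5% |
| Barnard, unpooled | 79.5% | 4.7% |
| Boschloo | 85.1% | 4.7% |

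At a common rate of 92.3%, Fisher's size is 1.8%. With control infection at 96.4% and vaccinees still at 51.3%, Fisher gives 92.9% and pooled-score Barnard 93.9%.

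**Step 3: per timepoint, same infection rates.**

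| Vaccinees v controls | Fisher | Barnard, pooled score |
|---|---|---|
| 20 v 13 (combined) | 67.7% | 78.3% |
| 19 v 13 (combined) | 68.3% | 74.8% |
| 20 v 7 (own cohort) | 34.6% | 55.4% |
| 19 v 7 (own cohort) | 28.3% | 50.3% |
| 20 v 6 (own cohort) | 23.2% | 36.9% |
| 19 v 6 (own cohort) | 18.4% | 41.4% |

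The gain is 6 to 11 points with combined controls and 14 to 23 points with own-cohort controls. Pooled-score Barnard's maximum size stays below 5% in every row (largest 4.9%).

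**Side check.** Section 9.2 also says 10/45 against 0/15 is significant at two-sided 0.05. Fisher, which section 9.4.4 specifies for adverse events, gives p = 0.0535; Barnard gives p = 0.049. This too suggests that the planning figures did not come from Fisher.

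**The case against.** A reader might infer that the protocol miscalculated its power, and that the trial has 79% primary power where it claims 83%. The documents do not support that. Fisher is written into the secondary paragraph only, the primary paragraph and 9.2 name no test, and 83% is correct for the pooled normal approximation. The 79.5% applies only if Fisher is carried over to the primary.

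A reader might also infer that Barnard is far stronger at each timepoint. That fits own-cohort controls. With combined controls, the set the primary paragraph uses, the gain is moderate.

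The rest of the opposing case is that Fisher is valid and widely accepted, that being conservative is not an error, and that the sponsor expects VE above the planning value. If 30% of vaccinees were infected (an assumption, lying between the planning 51% and the 2/12 implied by the earlier German trial cited in 2.1.5.1), and controls stayed at 92.3%, Fisher against Barnard would be 98.9% against 99.5% for the primary and about 97% against 98% for 20 v 13. Even 19 v 6 would give 72% against 84%. Section 9.4.1 also leaves room for a SAP with minor differences from the protocol.

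Most of this stands. No conclusion drawn with Fisher would be invalid, and the primary result is unlikely to turn on the choice. It does not repair the rationale, supply the missing primary test, or settle the control set, and the sample size was justified at the planning rates.

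**Conclusion.** The point holds as a gap in specification with a moderate cost in power. The reason given for Fisher is not a reason to use it, and the primary comparison has no named test. At the planning rates the difference for the primary is about 3 points (79.5% against 82.7%), falling to 1 point if control infection is 96.4%.

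For the per-timepoint analysis the loss is 6 to 11 points or 14 to 23 points, depending on a control set the plan leaves open. These figures assume an even split of drop-out and the planning infection rates at both timepoints. The control set matters more than the test: with 6 or 7 own-cohort controls even pooled-score Barnard reaches only 37% to 55%, so a change of test would not on its own justify calling that comparison powered.

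**What to change.** In 9.4.3, name one unconditional exact test for both the pooled primary and the per-timepoint comparisons of vaccinees with controls, and state its version: two-sided Barnard with the pooled score statistic, or Boschloo. The version matters because unpooled Barnard gives no more primary power than Fisher (79.5%). State whether each timepoint uses its own controls or all of them. Delete both sentences that justify the choice of test.

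In 9.2, attach the power to the chosen test: 83% for pooled-score Barnard, 85% for Boschloo, or 79% if Fisher is to be used for the primary. Give the per-timepoint power as well, or drop the description of it as powered in 4.4.

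The cost is protocol or SAP wording before database lock and a standard software option. The one drawback is a p-value that some readers will find less familiar.

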Intercurrent Events: Because three injections according to a defined schedule are presumed to be required to induce an optimal immune response, failure to fully immunize according to schedule constitutes an important intercurrent event potentially affecting the outcome variable. This can happen through a partial immunization (IV administration of less than 80% of the intended 0.5 mL dose), administration of one or more doses outside the specified immunization windows or by missing one or more immunizations. At this point, we have no data to indicate that missing any one of the three planned doses has a significantly different effect than missing any of the other doses, or that immunization outside of the protocol specified immunization windows is significantly different than immunization according to the immunization windows. Consequently, there are only three strata with respect to this intercurrent event: receiving three doses per protocol, receiving three doses but not per protocol, or receiving only two doses but remain in the trial and, in the judgement of the investigative team, may proceed to CHMI (see below and also see the Statistics section for population definitions).

Another intercurrent event that can affect the primary protection outcome is an inadvertent switch in treatment (from vaccine to placebo or vice versa due to clinical or pharmacy error). This has never occurred in a CHMI study of PfSPZ Vaccine, although it has occurred rarely in field studies. However, should it occur, any individual designated as a placebo recipient who inadvertently receives PfSPZ Vaccine

will be included in the vaccine population, following an “as treated” approach, even if only one dose of PfSPZ Vaccine is received.

Another variable that could influence outcome is the administration of drugs with antimalarial properties; for this reason, concomitant medications are carefully monitored, and participants are educated regarding the importance of communicating to the study staff all drugs taken outside the context of the study. Although surreptitious use of antimalarial drugs has occurred in the past, historically this has been a rare event.

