6.6 MEASURES TO MINIMIZE BIAS: RANDOMIZATION AND BLINDING

6.6.1 RANDOMIZATION

On the day of first immunization (V1 = study day 1), each participant invited to enroll will be randomized to receive PfSPZ Vaccine or NS according to a 3:1 ratio with randomization blocked to assure an approximation of this ratio in each CHMI cohort.

In the situation where an eligible participant withdraws consent or is deemed to be ineligible after treatment assignment but prior to administration of the first dose (e.g. due to acute illness or a request to withdraw from participation), a back-up participant will be assigned the same randomization number in the place of the participant who has become ineligible or has withdrawn consent. The withdrawn participant will be considered a screening failure, and the replacement participant will assume the randomization number of the withdrawn participant in order to assure that the study group receives the correct number of vaccine and placebo assignments. Once an injection has been given, however, even if the study participant withdraws immediately thereafter, the randomization number will not be reused, and the individual will be considered a drop-out.

The randomization procedure will be conducted by the data management and statistics vendor for this trial, as described in the applicable SOPs. Access to the unblinded randomization list will be limited exclusively to the syringe preparation team and the independent statistician(s) at the data management vendor. These individuals will be unblinded and will not be involved in evaluation or care of the study participants. A copy of participant treatment assignments will be retained at the site in a secure file by the unblinded Pharmaceutical Operations staff.

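### The ITT sensitivity analysis gives missing CHMI outcomes the same value in both arms, so it is only a partial check and does not bound the primary VE

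*Combined protocol and SAP*

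**What the plan says.** The primary VE is computed in the mITT population, which section 9.3.4 limits to participants who receive all three immunizations and undergo CHMI. Section 9.4.3 adds ATP and ITT sensitivity analyses. For ITT, "CHMI outcome will be imputed first as not protected for all individuals not undergoing CHMI, and then as protected", and the result is meant to indicate how robust the primary VE is. The rule does not depend on arm.

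Section 9.2 fixes the planning case: "Sample sizes of 45 and 15 for the vaccine and placebo groups were selected to be able to show with 83% power". Its assumptions are 6 vaccinees and 2 controls lost before challenge, then 12/13 controls and 20/39 vaccinees infected, for a VE of 44.4%.

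The text is not consistent on who will lack an outcome. Section 9.3.4 imputes people with one or two doses: "Because individuals will not be permitted to proceed to CHMI if they have not received three vaccinations". Section 3.1 (Intercurrent Events) lists as a stratum those "receiving only two doses but remain in the trial and, in the judgement of the investigative team, may proceed to CHMI". Section 3.1 (Development of an Estimand) first defines ITT by receipt of at least one immunization, then describes the ITT analysis in terms of at least one dose of PfSPZ Vaccine, which could be read as the vaccine arm only.

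**The concern.** The mITT analysis leaves out randomized, dosed participants who never reach CHMI. ATP is a subset of mITT and cannot speak to them, so the ITT imputation is the only stated check on what their missing outcomes could do. Missing outcomes move a risk ratio most when they differ between arms, and that is the case the plan does not examine. Section 3.1 argues that drop-out is unlikely to depend on arm. That is plausible under blinding, but it is an assumption, and same-direction imputation does not test it.

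The protected scenario has a second weakness. It scores unchallenged placebo recipients as protected, while section 3.1 describes near-universal susceptibility (27/28 infected).

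At stake is how the reported range is read. Two estimates of 38.1% and 44.4%, both significant, could be taken as bounds on the primary result, and they are not.

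**Working it through.** **Inputs.** Section 9.2: 45 and 15 randomized; 6 and 2 lost before CHMI; 20/39 and 12/13 infected; two-tailed alpha 0.05. Section 9.1.1: VE = 1 − risk ratio. P-values below are two-tailed Fisher, the test that 9.4.3 names for its secondary analysis (no test is named for the primary). Intervals are Wald on the log risk ratio.

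**The plan's own figures.** VE = 1 − (20/39)/(12/13) = 1 − 0.513/0.923 = 44.4%. Power = Φ[(|p1 − p2| − 1.96·SE0)/SE1], with SE0 pooled and SE1 unpooled: (0.410 − 1.96 × 0.156)/0.109 = 0.96, giving 83.2%. Both stated figures are reproduced.

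**The two planned scenarios.**
- mITT: 20/39 v 12/13, VE 44.4% (95% CI 21.6 to 60.6), p=0.009.
- All missing protected: 20/45 v 12/15, VE 44.4% (16.0 to 63.2), p=0.020. The vaccine risk is multiplied by 39/45 and the control risk by 13/15. Both equal 0.867, so the risk ratio cannot change, whatever the infection counts.
- All missing not protected: 26/45 v 14/15, VE 38.1% (17.8 to 53.4), p=0.012.

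**Imputing the arms separately.** Let i of the 6 missing vaccinees and j of the 2 missing controls be infected. Then VE = 1 − [(20+i)/45]/[(12+j)/15], which gives 7 × 3 = 21 cells:

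| i | j=0 | j=1 | j=2 |
|---|---|---|---|
| 0 | 44.4% (0.020) | 48.7% (0.006) | 52.4% (0.0008) |
| 1 | 41.7% (0.036) | 46.2% (0.008) | 50.0% (0.002) |
| 2 | 38.9% (0.041) | 43.6% (0.015) | 47.6% (0.002) |
| 3 | 36.1% (0.071) | 41.0% (0.017) | 45.2% (0.005) |
| 4 | 33.3% (0.079) | 38.5% (0.031) | 42.9% (0.005) |
| 5 | 30.6% (0.128) | 35.9% (0.035) | 40.5% (0.011) |
| 6 | 27.8% (0.215) | 33.3% (0.061) | 38.1% (0.012) |

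The plan computes only the top-left and bottom-right cells. They span 44.4 − 38.1 = 6.3 points of a possible 52.4 − 27.8 = 24.6. The worst case (26/45 v 12/15) has a 95% CI of −3.1 to 49.4; the best case (20/45 v 14/15) has 32.2 to 66.6. Five cells have p above 0.05: four with j=0 and one with j=1. None has j=2.

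**Unequal drop-out.** Using whole-number counts nearest the planned rates:
- 5 vaccine and 3 control missing: mITT 21/40 v 11/12, VE 42.7%. Protected: 21/45 v 11/15, VE 36.4%, p=0.084. The risk ratio is multiplied by (40/45)/(12/15) = 1.11, because a larger share of controls is scored as protected.
- 8 and 0 missing: mITT 19/37 v 14/15, VE 45.0%. Protected: 19/45 v 14/15, VE 54.8%.

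**The vaccine-arm-only reading.** If only vaccinees were imputed, VE would be 1 − (26/45)/(12/13) = 37.4% or 1 − (20/45)/(12/13) = 51.9%, and neither equals the mITT value.

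**The case against.** A reader might infer that neither planned scenario tests robustness. The figures do not support that: the not-protected scenario lowers VE by 6.3 points, and the protected one widens the interval and moves p from 0.009 to 0.020.

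A reader might also infer that the reported range will be narrow whatever the missing data do. That fails as well. The exact match needs equal drop-out fractions, and six and two is a planning assumption. If 8 of 60 dropped out at random, that split would have probability C(45,6)·C(15,2)/C(60,8) = 0.33. With other splits the protected scenario moves and can lose significance.

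The strongest objection is that the plan already contains the realistic low end. If missing controls are taken as infected, as the 27/28 figure suggests, the least favourable cell is 38.1% (p=0.012), which is the planned not-protected scenario. Every non-significant cell needs a missing control scored as protected. This stands, and it rules out reading 27.8% as a likely result. It does not make the planned pair a bound, and the pair omits the upper end of that same column (52.4%).

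It is also fair that section 3.1 attributes the choice of mITT to regulatory advice, that ITT VE is an exploratory objective, and that the detailed SAP was still to be finalized before database lock. These limit the weight of the point and make it easy to act on.

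**Conclusion.** The point holds as a limitation of an otherwise reasonable check. At the planned result and planned drop-out, one scenario cannot move the VE estimate and the other lowers it to 38.1%, while separate imputation spans 27.8% to 52.4%. With missing controls infected, the range is 38.1% to 52.4% and all seven cells are significant.

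This rests on the both-arms reading of ITT, which 9.3.4 and 9.4.3 support, on the infection counts in 9.2, and on Fisher's test. It does not show that the primary conclusion is fragile. With a larger effect the worst case need not overturn it: at an assumed 15/39 v 12/13 infected (mITT VE 58.3%), the worst case is 21/45 v 12/15, VE 41.7%, p=0.036.

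The conflict between 3.1 and 9.3.4 over two-dose participants is a separate defect. It leaves open who has a measured outcome and who is imputed.

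**What to change.** 1. Keep the two planned ITT scenarios and impute the arms separately as well. Add at least the two opposite-direction scenarios, or a tipping-point table such as the 21-cell one above, sized to the actual drop-out.
2. Present as the main reading the cells with missing controls infected, with missing vaccinees varied from all infected to all protected. Show the opposite-direction worst case as the outer bound, and say that it requires unchallenged controls to be scored as protected.
3. Reconcile section 3.1 (Intercurrent Events) with section 9.3.4 on whether two-dose participants may proceed to CHMI. Which rule applies is for the sponsor to settle.
4. Align the phrase about at least one dose of PfSPZ Vaccine in section 3.1 (Development of an Estimand) with the both-arms ITT definition in 9.3.4.

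This needs no new data, only a few lines of code and text in the SAP. The price is a wider reported robustness range.
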